12.3.3.1 Multiple Imputation for the Primary Efficacy Endpoint Analysis

Missing data can have an adverse effect on the estimation of endpoints. As such, multiple imputation for missing data will be used for the Primary Efficacy Endpoint analysis. Imputation will be performed under the assumption of missing at random (MAR) and supported by contemporary imputation under the assumption of missing not at random (MNAR). In addition, retrieved drop-out based multiple imputation will be explored whereby data from subjects who prematurely discontinue study drug treatment but remain in the study and still have assessments collected at the remaining scheduled visits in the study as used as the basis for imputation.

Thus, in the event of missing GC HCe values at Weeks 3, 6, 12 18 and 24, data will be imputed as follows:

(a) MAR Imputation

Step 1: Non-monotone missing data will be imputed first based on the MAR assumption via a multivariate joint Gaussian imputation model using Markov chain Monte Carlo (MCMC) method using the MCMC statement in the SAS® PROC MI procedure. Twenty imputed datasets will be produced. As a result, each imputed dataset will only have missing data at the end of subjects' records, (i.e. a monotone missing data pattern). The MCMC method in the MI procedure will be used with multiple chains (option CHAIN=MULTIPLE), 100 burn-in iterations, and a non-informative prior to imputed the remaining missing data. A separate imputation model will be used for each treatment arm. The imputation models will include GC HCe values at baseline and Weeks 3, 6, 12 and 18, sex, baseline GC type and baseline and CAH Type. In case

of non-convergence or non-estimability issues, a ridge prior and a single model will be considered with treatment arm added as explanatory variable to the model.

Step 2: The remaining, monotone, missing data for all subjects who discontinue study prematurely will be imputed using sequential regression multiple imputation model by randomised treatment arm. Each sequential regression model (i.e., for imputation of values at a given time point) will include the same explanatory variables as in Step 1 and all prior GC HCe values.

Step 3: The change from baseline in GC HCe to each scheduled post-baseline visit will be calculated, based on observed and imputed data. Each of the imputed complete datasets from Step 2 will be analysed with the same MMRM model used for the Primary Efficacy Endpoint ([Section 12.3.3](#)).

Step 4: The results of the analysis of each imputed dataset, i.e., treatment differences and their standard errors, will be combined using Rubin's imputation rules ([Rubin, 1987](#)) to produce pooled estimates of treatment differences, its 95% confidence interval and a pooled p-value. This will be done using SAS® MIANALYZE procedure.

(b) MNAR Imputation

Step 1: as (a)

Step 2: The remaining, monotone, missing data for all subjects who discontinue study prematurely will be imputed using sequential regression multiple imputation model estimated based on data from the *placebo arm only*. This will be achieved via the MNAR option in PROC MIANALYZE/ Each sequential regression model (i.e., for imputation of values at a given time point) will include the same explanatory variables as in Step 1 and all prior GC HCe values.

Step 3: as (a)

Step 4: as (a)

(c) Tipping Point MNAR Imputation

In the event the Primary Efficacy Endpoint is met, a Tipping Point analysis will be conducted. This will assess the robustness of the Primary Efficacy Endpoint analysis by determining the degree of penalty this is required to be applied to the active treatment arm to lose statistical significance. An increasingly punitive penalty will be determined as a small fraction of the 24 Week treatment effect estimate from the Primary Efficacy Endpoint analysis; i.e., if the treatment effect estimate from the Primary Efficacy Endpoint analysis of GC HCe is $\hat{\theta}$, then the penalty parameter, δ_{min} , will be set as $\delta_{min} = 0.05 \cdot \hat{\theta}$; and the maximum penalty parameter will be set as $\delta_{max} = 40 \cdot \delta_{min} = 2 \cdot \hat{\theta}$. Missing data will then be imputed as in (a) above, firstly applying no penalty (=Primary Efficacy Endpoint analysis assuming MAR) and then applying an increasingly punitive penalty ($\delta_{min}, \delta_{max}$) at intervals of 0.05 creating twenty imputed datasets. Each of these datasets will be analyzed as per Steps 3 and 4 in (a) above.

The p-values outputted from the application of each penalty value will be displayed along with the treatment effect estimates and associated CIs so that the tipping point resulting in loss of significance for the Primary Efficacy Endpoint can be identified. If the initial penalty parameters tested do not identify the tipping point, the process will be repeated with different penalty parameter values (e.g., $\delta_{min} = 0.04 \cdot \hat{\theta}, \dots, \delta_{min} = 0.01 \cdot \hat{\theta}$) until the tipping point is identified.

(d) Retrieved Dropout Imputation

Step 1: as (a)

Step 2: If $n \geq 5$ subjects in a treatment group have discontinued in each treatment arm, the remaining monotone missing data will be multiply imputed using a retrieved dropout approach via fully conditional specification and predictive mean matching assuming missing not at random (MNAR). The Markov chain Monte Carlo method with a non-informative prior (Jeffreys) will be used to perform a monotone-data imputation (IMPUTE=MONOTONE) by randomized treatment group.

Step 3: Week 24 GC HCe dose will be imputed using a set of predictors resulting in a set of linear coefficients b ,

Week 24 GC HCe dose

$$\begin{aligned} &= Treatment + Sex + Visit + Treatment * Visit \\ &+ \log(Baseline A4) + Baseline GC Dose + Baseline GC Type \\ &+ Baseline CAH Type + Last available GC HCe dose \end{aligned}$$

Step 4: Do a random draw from the *posterior predictive distribution* of b producing a new set of coefficients b^* . Use b^* to generate predicted values for the Week 24 for all subjects.

Step 5: For each missing Week 24 value, identify a set of candidates with observed Week 24 values whose predicted values are close to the predicted value for the case with missing data. From the candidates, randomly choose one Week 24 value and assign its observed value to the missing value. Repeat process for every subject with missing data.

The analysis methods described in [Section 12.3.3](#) will be applied to the imputed datasets.

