4.1.4.3 A4-Based Daily Glucocorticoid Dose Adjustment Algorithm

Any adjustment of GC dose will be based on the A4 level measured at study visits and made in increments ≤ 5 mg/day HCe according to the standardized sets of GC regimens ([Table 1](#)).

The below A4-based algorithm will be used to guide changes to GC replacement therapy. Reductions below 15 mg/day should be discussed with the Medical Monitor.

A4 Level ≤ULN

- Reduce GC dose
- GC dose reductions may begin on Week 2 (based on Day 1 measurement) and thereafter at Week 6, 12, 18, 24, 32, 40, 52, and 64 study visits, or during the optional Open-Label Extension Period

A4 Level >1.25x ULN

- Increase GC dose
- GC dose increases can occur at Week 6, 12, 18, 24, 32, 40, 52, and 64 study visits, or during the optional Open-Label Extension Period

A4 level >ULN and ≤1.25x ULN

- Maintain GC Dose

The Investigator should contact the Medical Monitor if the Investigator does not intend to follow A4-based GC dose adjustment algorithm at a visit.

The daily GC dosing frequency (e.g., BID or 3 times daily [TID]) should remain stable throughout the study. The Investigator should contact the Medical Monitor if the Investigator intends a change to the GC dosing frequency at a visit.

If a change in GC is warranted by the A4 algorithm, sites will contact subjects by telephone within 2 weeks after each applicable study visit. If no GC dose adjustment is warranted based on the A4 level, the site does not need to contact the subject.

Sites will telephone subjects again 7 days after GC dose adjustment to assess for the occurrence of AEs and the initiation of new concomitant medications.

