4.3.1 Efficacy Assessments

4.3.1.1 Hormone Assessments

All blood samples for hormones and androgens will be collected at approximately 8 AM (7- 9 am window) prior to administration of a subject’s morning GC dose. A4, 17-hydroxyprogesterone (17-OHP), adrenocorticotropic hormone (ACTH), and testosterone will be measured. Hormone assessments will be collected at all study visits except for Week 3 (safety laboratory assessments only).

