6 SAMPLE SIZE AND POWER

The original sample size calculation was based the binary endpoint of percent of subjects with a 5 mg/day HCe reduction from baseline in GC dose at Week 24 with $A4 \leq \text{ULN}$. Assuming a

placebo group response of 30%, N = 45 subjects per group would provide at least 90% power to detect a between group relative difference of 33% at the 0.05 two-sided type I error rate.

Additionally, it was computed that a sample size of N=45 subjects per group would provide at least 90% power to detect a mean change in daily GC dose from baseline and placebo of 7.25 mg/day in HCe, assuming a standard deviation (SD) of 10.5 mg/day HCe and the two-sided type I error is 0.05. Examination of group blinded data, provides a conservative SD estimate of 6.9 mg/day. On this basis, a sample size of N=40 subjects per group provides at least 90% power to detect a mean change in daily GC dose from baseline and placebo of 5 mg/day in HCe with a two-sided type I error of 0.05.

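### No imputation scheme for the primary endpoint uses post-baseline A4, the main trigger of the next dose step: possible modest bias and some lost precision

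*SAP*

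**What the plan says.** **Imputation.** SAP 12.3.3.1 plans four schemes for missing GC dose. Step 1 of the missing-at-random scheme (a) reads: "The imputation models will include GC HCe values at baseline and Weeks 3, 6, 12 and 18, sex, baseline GC type and baseline". The sentence goes on to CAH type. The last quoted word has no noun after it, so a term may have dropped out. Step 2 of (a) takes the same predictors plus all prior doses. Scheme (b) does the same with a model fitted to placebo only. Scheme (c) imputes as in (a) and adds a penalty to the active arm. Scheme (d) includes log baseline A4 and the last available dose, but no later A4. The MMRM in SAP 12.3.3 has no A4 term.

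**Dosing.** Protocol 4.1.4.3: "Any adjustment of GC dose will be based on the A4 level measured at study visits". The dose goes down at or below ULN, is held up to 1.25 x ULN and goes up above that, by at most 5 mg/day HCe per step. Sites telephone within 2 weeks of the visit, so the Week 18 A4 governs the dose held at Week 24. SAP 4.2.2.1 lets clinical judgement override the algorithm.

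**A4 data.** SAP 4.3.1.1: "Hormone assessments will be collected at all study visits except for Week 3". A4 is therefore available at Day 1 and Weeks 6, 12 and 18, before the Week 24 endpoint.

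**The concern.** Take two subjects in one arm with the same dose history and the same sex, GC type and CAH type, who both leave after Week 12. One has A4 at 2 x ULN and is due an increase; the other has A4 at 0.5 x ULN and is due a reduction. Schemes (a) to (c) give them the same predictive distribution, although the algorithm can send them 10 mg/day apart at the next adjustment (5 up, 5 down).

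Loss of androgen control is a plausible reason to leave. If leaving tracks A4, the data are not missing at random given past dose, but may be so given past dose and A4. Scheme (a) has nearly the same variables as the MMRM and will mostly reproduce it, so agreement between the two would not be reassuring. Schemes (b) and (c) start from the same predictors.

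**Working it through.** **1. Scale, from SAP 6.** SE = SD x sqrt(2/n); power = Φ(difference/SE − 1.96).

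- The SAP says its blinded data "provides a conservative SD estimate of 6.9 mg/day" and that "a sample size of N=40 subjects per group provides at least 90% power to detect a mean change in daily GC dose", for a difference from "placebo of 5 mg/day in HCe with a two-sided type I error of 0.05". SE = 6.9 x sqrt(2/40) = 1.54; power = Φ(5/1.543 − 1.96) = Φ(1.28) = 0.900 (0.893 with the t distribution).
- The other calculation, with 45 per group and a target difference of 7.25 mg/day, is made "assuming a standard deviation (SD) of 10.5 mg/day HCe and the two-sided type I error is 0.05". SE = 10.5 x sqrt(2/45) = 2.21; power = Φ(7.25/2.214 − 1.96) = Φ(1.32) = 0.906.

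Both reproduce, and no stated figure is in dispute. At 45 per arm with SD 6.9, SE = 6.9 x sqrt(2/45) = 1.45. The working SE is about 1.5 mg/day.

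**2. What A4 adds.** Large-sample simulation, 200,000 per arm: 5 mg steps by the protocol algorithm at Day 1 (reductions only) and Weeks 6, 12 and 18, with a 15 mg floor. Assumed, because the documents do not give them: A4 distribution and noise, drug effect on A4, algorithm adherence, and dropout. Sex, GC type and CAH type were not simulated. Share of the variance of the Week 18-to-24 dose step explained:

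| Adherence | Dose history | Plus Week 18 A4 |
|---|---|---|
| 90% | 5% | 86% |
| 60% | 4% | 58% |

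**3. Dropout with fixed rates.** Bias in an arm mean = proportion missing x mean error per missing subject; bias in the difference = active − placebo. The true difference is −5.0 mg/day at 90% adherence. Positive bias means the benefit is understated. Slope is the log-odds of dropout per unit of log A4. Without A4 in the model:

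| Dropout, placebo/active | Link to A4 | Error per missing, placebo | Placebo bias | Active bias | Difference |
|---|---|---|---|---|---|
| 10/10% | slope 1, both | −2.18 | −0.22 | −0.19 | +0.03 |
| 20/20% | slope 2, both | −3.97 | −0.79 | −0.71 | +0.08 |
| 20/20% | slope 2, placebo only | −3.94 | −0.78 | −0.01 | +0.78 |
| 30/10% | slope 2, both | −4.15 | −1.24 | −0.35 | +0.90 |
| 20/20% | slope 2, opposite signs | −3.98 | −0.80 | +0.50 | +1.30 |

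Check on row 2: 0.20 x −3.97 = −0.79, and −0.71 − (−0.79) = +0.08. With equal rate and linkage the difference is off by +0.02 to +0.10 (up to +0.23 with a larger drug effect). With dropout unrelated to A4, or related only to past dose, bias is at most 0.06. Adding A4 brings the difference to within about 0.04.

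**4. Dropout by an A4 rule.** 300,000 subjects per scenario, the same rule in both arms, true effect −4.3 to −4.9.

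- Dropout of 10 to 15% per visit above 1.25 x ULN and 2% otherwise (8 to 18% per arm overall): bias +0.15 to +0.33.
- Dropout of 10% per visit at or below ULN (17 to 24% per arm): bias −0.10 to −0.19.
- With A4 in the model: within ±0.01.

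**5. Trial size, 45 per arm.** Under one set of assumed inputs, bias of +0.34 or −0.14 fell to about +0.03 when A4 was added. The RMSE of the difference fell by 3 to 4%, including when dropout was unrelated to A4. Under another set, +0.48 fell to +0.03 and −0.25 became +0.05; RMSE went from 1.95 to 1.91 and from 1.97 to 1.87. In that run the regression with A4 was singular until a ridge term was added.

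**6. Relative size.** 0.1/1.5 = 0.07 SE and 0.35/1.5 = 0.23 SE.

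**The case against.** The estimand follows treatment policy (SAP 12.3.1), and Protocol 7.1 commits to efforts to keep collecting data after study drug stops. The endpoint is the prescribed dose on the eCRF (SAP 4.3.1.2), and Protocol 7.2 expects withdrawals to be rare. Stopping drug is therefore not the same as missing data. This stands and limits the size, as does the comparison with the SE.

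The tipping-point analysis also probes departures from missing at random. To offset −0.19 with 17 to 24% missing, each imputed active value must shift by 0.19/0.24 = 0.79 to 0.19/0.17 = 1.12 mg/day. Against an effect near 4.6 that is 0.17 to 0.24 of the effect, or about four to five of the 40 steps of 0.05. This stands too, but the penalty acts only on the active arm and leaves the placebo arm uncorrected.

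The MMRM lacks A4 as well. That is no reason to leave A4 out of the imputation. As a post-randomisation covariate in the MMRM it would absorb part of the treatment effect, so the imputation model is the right place for it.

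A reader might infer that A4 fixes the next dose and that the planned analysis is therefore biased. The documents do not support this. Investigators may override the algorithm, SAP 12.6.5.6 summarises how often it was followed, and nothing in either document shows that missingness depends on A4. Nor do the models rest on dose history alone, since they include sex, GC type and CAH type; none of these carries current A4.

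**Conclusion.** The omission is real: no scheme uses post-baseline A4. Even if the incomplete sentence in (a) was meant to name baseline A4, that remains true. The bias is conditional. It needs missingness that depends on A4 given past dose. Under assumed dropout of about 8 to 24% per arm it is then roughly 0.1 to 0.35 mg/day in the treatment difference (0.48 under one set of inputs). The benefit is understated if subjects with high A4 leave and overstated if those with low A4 leave. It could reach +0.4 to +1.3 mg/day if the arms differ in dropout rate or in the strength or direction of the link. Arm means are affected more than the difference. A precision gain of a few percent in RMSE is available even without a link. All these sizes rest on assumed A4 behaviour, drug effect, adherence and dropout. This is a worthwhile improvement from data already collected, not a defect that invalidates the primary analysis.

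**What to change.** Before database lock, amend SAP 12.3.3.1:

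- **(a) Steps 1 and 2:** add the most recent A4 relative to ULN as an auxiliary variable: its log, plus the categories at or below ULN and above 1.25 x ULN where they can be estimated. Impute in visit order: dose at the next visit given dose history and current A4, then A4 at that visit.
- **(b) and (c):** carry the same terms over.
- **(d):** add the last available A4.
- Complete the unfinished predictor list in (a).

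With about 45 subjects per arm, keep the form parsimonious and use the ridge prior or the single model with treatment arm that Step 1 of (a) already allows.

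Cost: SAP wording, moderate programming and a few more parameters in a small-sample model. There are no new data and no change to the estimand or conduct. State in the SAP that (b) becomes less punitive, because A4 observed before dropout carries some of the drug effect. In the step 3 simulation with equal dropout and slope 1, adding A4 moved the (b) estimate from −4.60 to −4.83 at 10% dropout and from −4.19 to −4.67 at 20%.

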4.1 Randomization and Blinding

Subjects will be centrally randomized in a 1:1 ratio to receive tildacerfont at 200 mg QD or matching placebo using a randomization and trial supply management (RTSM) system. Randomization will be stratified by sex (male and female) and baseline GC dose level (< 40 mg/day and \geq 40 mg/day in HCe). Investigators, subjects, and the Sponsor will be blinded to assigned study drug for the duration of the Placebo-Controlled Treatment Period.

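### SAP 12.3.3.1: the tipping-point fallback names only smaller penalties, and the retrieved-dropout trigger counts subjects who may have no Week 24 dose

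*SAP*

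**What the plan says.** SAP 12.3.3.1(c) runs only if the primary endpoint is met. On scale it says: "An increasingly punitive penalty will be determined as a small fraction of the 24 Week treatment effect estimate". The smallest penalty is 0.05 times the estimate, and the largest is 40 times the smallest, which is 2 times the estimate. On failure it says: "If the initial penalty parameters tested do not identify the tipping point, the process will be repeated with different penalty parameter values". The values that follow, introduced as examples, reset the smallest penalty to 0.04 and on down to 0.01 times the estimate, and the process continues until a tip is found. No larger value, upper bound or no-tip result is given.

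The opening of 12.3.3.1 bases the retrieved-dropout method on subjects who stop study drug, stay in the study and are still assessed. The trigger in (d) is at least five subjects who "have discontinued in each treatment arm, the remaining monotone missing data will be multiply imputed using a retrieved dropout approach". Step 2 imputes by treatment group, yet the Step 3 model contains Treatment, Visit and their interaction. Step 5 tells the analyst to "identify a set of candidates with observed Week 24 values whose predicted values are close", without limiting candidates to subjects who are off drug.

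**The concern.** A tipping-point analysis asks how bad the unobserved outcomes would have to be before significance is lost. If the largest planned penalty does not remove significance, the search has to go to larger penalties; the named values go the other way. Any upward extension would then be chosen after a significant result has been seen, since (c) runs only in that case.

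In (d), the trigger and the method refer to different people. Five subjects per arm may have discontinued with none observed at Week 24. The trigger also does not say whether discontinuation means study drug or study. SAP 12.3.4.1.1 reports results for (a) to (d), and Protocol 9.4.1 names retrieved dropout as the approach to missing data, so both analyses will be read as evidence on robustness.

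**Working it through.** **Inputs.** SAP 6: "a sample size of N=40 subjects per group provides at least 90% power to detect a mean change in daily GC dose", for a difference of 5 mg/day, "with a two-sided type I error of 0.05"; blinded data "provides a conservative SD estimate of 6.9 mg/day". SAP 4.1: "Subjects will be centrally randomized in a 1:1 ratio". No missing-data rate is given. Protocol 7.2 expects withdrawal to be uncommon, so I assume that a share m of 5% to 30% of the active arm is imputed.

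**The plan's own figure.** SE = 6.9 × √(2/40) = 1.543, and z = 5/1.543 = 3.24. Normal-approximation power is 0.8999 (noncentral t 0.893), so the stated 90% is reproduced to rounding.

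**Grid arithmetic.** 40 × 0.05 = 2.0. If the 40-fold rule carries over, the named fallbacks have maxima of 40 × 0.04, 0.03, 0.02 and 0.01 = 1.6, 1.2, 0.8 and 0.4 times the estimate. If the ceiling instead stays at 2, the grid is only finer. Neither reading tests anything above 2.

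**Where the tip lies, in closed form.** Worsening the imputed active-arm doses by k times the estimate leaves an effect of θ(1 − mk).
- With the SE held fixed, the tip is k = (1 − 1.96/3.24)/m = 0.395/m.
- If the shift also adds m(1 − m)(kθ)² to the active-arm variance, the tip comes earlier. Check at m = 10%, k = 3.25: effect 5 × 0.675 = 3.375; active variance 47.61 + 0.09 × 16.25² = 71.4; SE = √((47.61 + 71.4)/40) = 1.725; ratio 1.96.

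| Active arm imputed (assumed) | Tip, inflated to fixed SE (× estimate) |
|---|---|
| 5% | 5.7 to 7.9 |
| 10% | 3.3 to 4.0 |
| 15% | 2.3 to 2.6 |
| 20% | 1.8 to 2.0 |
| 30% | 1.2 to 1.3 |

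A penalty of 2 times the estimate therefore does not tip unless about 18 to 20% of the active arm is imputed. At the SAP's other design point (7.25 mg/day, SD 10.5, 45 per arm) the threshold is 18.5 to 20.5%. For a barely significant result (3.2 mg/day, SD 6.9, 45 per arm, z = 2.2) it falls to about 5%.

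**Simulation.** Trials were drawn at 5 mg/day, SD 6.9 and 40 per arm. In the significant ones, the missing share of the active arm was shifted in steps of 0.05 times the estimate until the two-sample t-test gave p ≥ 0.05.

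| Missing (assumed) | Median tip (× estimate) | Tip above 2 times |
|---|---|---|
| 5% | about 5.7 | about 96% |
| 10% | about 3.4 | about 82% |
| 15% | about 2.4 | about 68% |
| 20% | about 1.9 | about 42% |

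**Retrieved dropout.** Within one arm at Week 24, Treatment, Visit and their interaction are constant. The literal design has 10 columns and rank 7: intercept, sex, log baseline A4, baseline dose, GC type, CAH type and last available dose. Five subjects give rank 5 at most, and at least 8 are needed for one residual degree of freedom. Pooling the arms at 5 + 5 gives 8 coefficients and 10 − 8 = 2 residual degrees of freedom.

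If a share r of discontinuers is observed at Week 24, the chance that five discontinuers in an arm yield no donor is (1 − r)⁵. That is 0.8⁵ = 33% at r = 20% and 0.6⁵ = 8% at r = 40%; both values of r are assumptions.

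**The case against.** The fallback values are examples. The governing instruction is to try different values until a tip is found, so larger penalties are not forbidden. A reader might infer that the procedure can never find the tip; the text does not support that. What stands is that every value it names is useless for this purpose and that it has no stopping rule.

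A reader might also note that the estimate is tildacerfont minus placebo, hence negative for benefit, and infer that the penalty would improve the active arm. The SAP says the penalty is punitive and is applied to the active arm until significance is lost, so the direction is set in words. Stating the sign is only a clarification.

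A run with no tip is still informative: p-values and intervals are displayed at each penalty, and significance held to 2 × 5 = 10 mg/day worse than the missing-at-random imputation is a meaningful result. Some larger shifts may also be implausible. Protocol 4.1.4.3 allows increases of at most 5 mg/day after each of Weeks 6, 12 and 18, or 15 mg/day in all, whereas 5.7 × 5 = 28.5 mg/day. That favours a stated bound. It does not favour stopping at 2 times, because the 15 mg/day is counted from the dose before those increases and the penalty from the imputed dose.

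On (d), the model is inestimable only if it is fitted by arm to retrieved dropouts alone. The Treatment term in Step 3 suggests pooling, and a pooled 5 + 5 model can be fitted, though thinly. With all observed subjects as donors it can also be fitted, but it then borrows from on-drug completers and is not a retrieved-dropout analysis. The SAP does not say which is meant.

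**Conclusion.** The point holds as a specification fault in two supportive analyses and should be corrected. In (c), the ceiling is 2 times the estimate, every named fallback is smaller or finer, and no no-tip outcome exists. At the SAP's 5 mg/day, SD 6.9 and 40 per arm, the tip lies above that ceiling in roughly 4 in 5 significant trials or more at 5 to 10% missing, and in about 2 in 5 at 20%. These figures rest on assumed missing rates and a t-test approximation, not the planned MMRM with Rubin pooling. They would be lower for a weakly significant result.

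In (d), the trigger counts discontinuations although the method needs off-drug subjects with observed data, and the text leaves both pooling and donors undecided. It would be wrong to infer that (d) always fails or that the primary result is compromised. The SAP describes (d) as explored, (a) and (b) stand, and the primary test, its alpha and its estimand do not change.

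**What to change.** **(c)** Replace the fallback with an upward extension: keep the step at 0.05 times the absolute value of the estimate, and raise the maximum until p ≥ 0.05 or a plausible bound on the imputed dose, stated by the sponsor in advance, is reached. If none is found, report no tip up to that bound. State that the penalty is scaled to the absolute estimate and added to imputed active-arm GC dose, and give the unit of the 0.05 interval.

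**(d)** Trigger on the number of subjects off study drug with an observed Week 24 dose, and restrict donors to them. Pool the arms with treatment as a covariate, and reduce the predictors, for instance to baseline dose and last on-drug dose. With an intercept and treatment that is 4 coefficients, leaving 10 − 4 = 6 residual degrees of freedom at 5 + 5. Below the threshold, rely on the placebo-based imputation in (b).

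The cost is SAP wording and a longer programmed grid, settled before database lock and unblinding. No data collection changes.

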9.4 Statistical Analyses

9.4.1 General Considerations

All individual data will be listed as measured. All statistical summaries and analyses will be performed using SAS software (SAS Institute Inc, Cary, North Carolina, USA).

Unless otherwise specified, continuous adrenal biomarkers (A4, 17-OHP, ACTH) will be summarized using a 11-point descriptive statistics (i.e., n, mean, standard deviation [SD], median, 25% quartile [Q1], 75% quartile [Q3], minimum, maximum, geometric mean, geometric coefficient of variance [CV%], 95% confidence interval [CI] for geometric mean [including geometric mean ratio and its 95% CI]). Continuous data aside from (A4, 17-OHP and ACTH) will

be summarized using an 8-point descriptive summary (n, mean, SD, median, Q1, Q3, minimum, and maximum).

Categorical data will be summarized using the frequency of events and percentage of total events.

Data will be presented by treatment group. Changes in primary, secondary, and exploratory endpoints will be analyzed over time, with change from baseline summarized for each post-baseline time point measured.

All efficacy analyses will be conducted using the ITT Population as the primary analysis set and using a 2-sided alpha of 0.05.

For missing data, a retrieved dropout approach will be used in which missing endpoint data for subjects who discontinued early will be imputed using data collected from subjects after discontinuation of study drug.

Secondary and exploratory analyses that evaluate the change from baseline in all subjects after 52 weeks of tildacerfont treatment will combine the subjects randomized to tildacerfont Day 1 to Week 52 data with subjects randomized to placebo tildacerfont treatment data from Week 24 to Week 76.

Any changes to the protocol-specified analyses will be pre-specified in the SAP prior to database lock.

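### Method (d) in SAP 12.3.3.1 gives retrieved dropouts no special role, so it runs close to missing-at-random imputation despite its MNAR label

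*SAP*

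**What the plan says.** Protocol 9.4.1 names a retrieved-dropout approach for missing data: "missing endpoint data for subjects who discontinued early will be imputed using data collected from subjects after discontinuation of study drug". SAP 12.3.3.1 repeats the intent, taking as the basis for imputation "data from subjects who prematurely discontinue study drug treatment but remain in the study and still have assessments collected". It says this will be explored in addition to MAR method (a) and the MNAR methods.

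The algorithm under (d) reads as follows:

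- **Step 2** switches the method on if at least 5 "subjects in a treatment group have discontinued in each treatment arm". It specifies predictive mean matching by randomized group and labels the assumption MNAR.
- **Step 3** models the Week 24 dose on treatment, sex, visit, treatment by visit, log baseline A4, baseline GC dose and GC type, ending with "Baseline CAH Type + Last available GC HCe dose".
- **Step 4** draws coefficients and generates predictions for all subjects.
- **Step 5** says, for each missing value, to "identify a set of candidates with observed Week 24 values whose predicted values are close to the predicted value for the case with missing data", and then to copy the observed dose of one candidate chosen at random.

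SAP 12.3.1 sets a treatment-policy estimand that ignores discontinuation. Protocol 7.1 plans continued data collection, where possible, after study drug is stopped.

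**The concern.** Under a treatment-policy estimand, the missing Week 24 dose of a subject who stopped drug and left is an off-drug dose. Subjects who stopped drug but stayed are the natural source of information about it, and both documents say so. In Steps 3 to 5 nothing separates these subjects from those still on drug. Discontinuation appears only in the trigger.

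An off-drug rise is plausible from the protocol itself: the A4 algorithm (Protocol 4.1.4.3) increases GC dose when A4 exceeds 1.25x ULN, and Protocol 4.3 gives a half-life of about 60 hours. Donors still on tildacerfont cannot represent such a rise. At stake is whether an analysis reported as an MNAR check says anything different from the MAR result. SAP section 3 makes the SAP govern over the protocol, and SAP section 14 (changes from the protocol) is not yet filled in, so no departure is declared.

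**Working it through.** **1. The plan's own figure.** SAP section 6 states that "a sample size of N=40 subjects per group provides at least 90% power" for "a mean change in daily GC dose from baseline and placebo of 5 mg/day in HCe"; the blinded data, it says, "provides a conservative SD estimate of 6.9 mg/day". n per arm = 2(1.960 + 1.282)² × (6.9/5)² = 2 × 10.51 × 1.904 ≈ 40.0, which rounds up to 41. Power at 40 is 0.8999 (normal) or 0.893 (noncentral t). The figure is reproduced within rounding. It gives two yardsticks: the planned 5 mg/day, and a simple standard error at 45 per arm of 6.9 × √(2/45) = 1.45 mg/day.

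**2. Intent against steps.** Intent: impute from off-drug data. Step 3: no off-drug term. Step 4: predictions for everyone. Step 5: eligibility rests only on an observed Week 24 value. Run by arm, this is predictive mean matching conditional on observed covariates and dose, which is an MAR method.

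**3. Two readings of the last-dose predictor.** The SAP does not define it for subjects whose Week 24 dose is observed. Literally, their last available dose is the Week 24 dose, so the outcome predicts itself. Alternatively, it is the last dose before Week 24. Both were simulated.

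**4. One arm.** All settings are assumptions: 45 subjects, stopping at Week 12, 7 missing at Week 24, 9 retrieved dropouts, 5 nearest donors, 1000 replicates. The alternative reading uses the Week 18 dose for completers and the Week 12 dose for those who stopped. The last column is a regression on the last on-drug dose, fitted to retrieved dropouts only. Entries are the mean Week 24 change in the missing subjects (mg/day).

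| Assumed off-drug rise | Truth | (d), literal | (d), dose before Week 24 | Retrieved only |
|---|---|---|---|---|
| 0 | −5.99 | −6.31 | −7.20 | −6.04 |
| 4 | −2.05 | −6.19 | −6.14 | −2.04 |
| 7 | +1.06 | −6.06 | −5.37 | +1.05 |
| 10 | +4.03 | −5.99 | −4.80 | +3.91 |

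Shift in the arm mean = 7/45 × error. At a rise of 7, literal: 7/45 × 7.12 = 1.1 mg/day. At no rise: 7/45 × 0.32 = 0.05 (literal) and 7/45 × 1.21 = 0.19 (alternative). On the literal reading the coefficient on last dose was 1.000 with residual SD 0. With 5 or 9 retrieved dropouts and 5 nearest donors, retrieved dropouts supplied 12–26% of donors.

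**5. Two arms.** 45 per arm, assumed 5 mg/day on-drug effect wholly lost on stopping, 400 trials × 10 imputations, 5 nearest donors. Entries are tildacerfont minus placebo (mg/day).

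| Stop drug / of whom retrieved | Truth | (d), literal | (d), dose before Week 24 | Donors restricted to retrieved |
|---|---|---|---|---|
| 20% / 50% | −4.01 | −4.37 | −4.40 | −4.03 |
| 30% / 50% | −3.36 | −3.87 | −3.89 | −3.37 |
| 30% / 30% | −3.49 | −4.24 | −4.32 | −3.60 |

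The literal reading overstates by 0.36, 0.51 and 0.75 (9%, 15% and 21% of the truth), the alternative by 0.39, 0.53 and 0.83. As a rough ceiling, fraction missing × 5 = 0.50, 0.75 and 1.05, so the results are of the expected order.

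**6. Trigger.** With exactly 5 discontinued in an arm, the chance that none is retrieved is 0.5⁵ = 3% at 50% retrieval and 0.7⁵ = 17% at 30%.

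**The case against.** The strongest reply is that (d) omits a restriction but is not a different method. The lead-in and Step 2 both call it retrieved-dropout, and Steps 3 to 5 read like a generic account of predictive mean matching that a programmer might apply to the right subset. That is fair about intent, but the written steps are what would be programmed.

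Several stronger inferences are tempting and do not stand:

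- **That (d) does not use retrieved dropouts.** They are in the fit and are eligible donors within their arm; they simply get no special role.
- **That (d) amounts to carrying the last on-drug dose forward.** This needs the literal reading of an undefined term. Even then it is approximate: imputed means fell within about 0.35 mg/day of carry-forward, and the last available dose may itself be off-drug. The two readings give almost the same bias, so the donor pool and fit drive the problem.
- **That the trigger could leave (d) without donors.** As written, on-drug subjects remain eligible. The 3% and 17% are chances of having no retrieved subject, which matters once donors are restricted.
- **That MAR would otherwise go untested.** Method (b) imputes from placebo, and (c) applies a tipping-point penalty if the primary endpoint is met. Observed off-drug doses also enter the main MMRM directly.

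The objection to the magnitude largely stands. Protocol 7.2 expects withdrawal to be uncommon, and no discontinuation rate is given. Scheduled GC adjustments before Week 24 follow Day 1 and Weeks 6, 12 and 18 in steps of at most 5 mg/day, so a subject who stops after the Week 18 adjustment may keep the same dose. Full loss of effect in every stopper is an adverse case, and the two-arm biases (0.36 to 0.83) are roughly a quarter to just over half of the 1.45 standard error.

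**Conclusion.** The mismatch is established from the text alone: (d) as written does not carry out the imputation that both documents describe, and it is close to MAR predictive mean matching under an MNAR label. If GC dose rises off drug, it overstates the treatment effect under either reading of the predictor.

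The size is conditional. The 0.4 to 0.75 mg/day on the literal reading (up to 0.83 on the other) assumes 20–30% discontinuation, 30–50% retrieval and complete loss of a 5 mg/day effect. With no off-drug rise the error is small. The documents supply none of these quantities.

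A reader might infer that the primary result is itself biased, or that (d) would falsely confirm it. The documents do not support that: the main MMRM is separate, (d) is exploratory support, and (b) and (c) also challenge MAR. What is lost is the one planned analysis meant to draw on real off-drug data. That merits correction before lock.

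**What to change.** In SAP 12.3.3.1(d):

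1. **Fit and donors.** Restrict both the Step 3 fit and the Step 5 candidates to subjects in the same arm who stopped study drug before Week 24 and have an observed Week 24 GC dose. Restricting donors alone would leave the model fitted mostly to on-drug subjects, for whom a predictor tied to discontinuation is undefined or equals the outcome.
2. **Predictor.** Define it as the GC HCe dose at the last visit on or before study drug discontinuation.
3. **Model.** Use that dose alone, or with baseline GC dose. About 5 subjects cannot support all the Step 3 terms. Drop treatment, visit and treatment by visit, which have no role in a by-arm model of one visit.
4. **Trigger.** Require at least 5 such retrieved subjects in each arm. Otherwise rely on placebo-based method (b).

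The cost is SAP wording and programming before lock, with no new data. The drawback is precision: few donors make this supporting estimate more variable, and with 5 donors and 5 nearest matches the matching becomes a random draw among them.
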